9.5.11 Acceptability of Insulin Delivery Experience

Acceptability of patient overall experience with the study insulin delivery will be summarized (yes/no) by treatment.

9.5.12 Other assessments

To determine catheter occlusion rates with LY900014 and Humalog after 3 days of CSII, the frequency of “occlusions observed on macroscopic examination of the catheter and catheter tubing” from the CRF will be.

All other safety assessments not detailed in this section will be listed but not summarized or statistically analyzed.

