To evaluate the difference in insulin lispro PK when LY900014 and Humalog are administered as different test bolus doses with an insulin pump to patients with T1DM during a breakfast meal test	AUC, C _{max} , T _{max} , early 50% T _{max} , and late 50% T _{max}
Secondary Objectives	Endpoints
To evaluate the sustainability of any difference in insulin lispro PK of LY900014 and Humalog over 3 days when administered as different test bolus doses with an insulin pump to patients with T1DM during a breakfast meal test	AUC, C _{max} , T _{max} , early 50% T _{max} , and late 50% T _{max}
To evaluate the difference in GD response when LY900014 and Humalog are administered as different test bolus doses with an insulin pump to patients with T1DM during a breakfast meal test	ΔAUC
To compare the durability of GD response over 3 days when LY900014 and Humalog are administered as different test bolus doses with an insulin pump to patients with T1DM during a breakfast meal test	ΔAUC
Exploratory Objectives	Endpoints
To evaluate the safety and tolerability of LY900014 administered with an insulin pump	Adverse events, anti-insulin lispro antibodies, infusion-site reactions/pain, and frequency and/or severity of hypoglycemia
To compare the GD response using CGM when LY900014 and Humalog are administered as different test bolus doses with an insulin pump to patients with T1DM during a standardized lunch meal	ΔAUC
To compare the GD response using CGM when LY900014 and Humalog are administered as different test bolus doses with an insulin pump to patients with T1DM during a standardized dinner meal	ΔAUC
To evaluate the intrasubject and intersubject insulin lispro PK variability of LY900014 compared with Humalog after 3 days of CSII	CV of AUC
To determine catheter occlusion rates with LY900014 and Humalog after 3 days of CSII	Microscopic assessment of infusion tubing after 3 days of use or in case of suspected catheter occlusion
To perform an exploratory comparison of glucose fluctuations with time in patients with euglycemia, hypoglycemia, and hyperglycemia receiving LY900014 and Humalog	CGM profiles during inpatient periods: time in euglycemia, hypoglycemia, and hyperglycemia

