5.1.1.4. Day 3 Activities

Before the start of the run-in period, the cannulation of 2 veins will be performed. On Day 3, approximately 7 hours before dosing (approximately 1:00 AM), the run-in period for the Day 3 MMTT will start. The run-in period, breakfast MMTT, and lunch meal procedures will be performed as described above for the Day 1 procedures.

If a catheter occlusion alarm occurs <5 hours after the start of the MMTT on Day 3, the data will not be used for analysis and the entire period can be repeated a maximum of 1 time. If catheter occlusion occurs >5 hours after the start of the MMTT on Day 3, the data will be used for analysis for the breakfast meal test, but the lunch test meal on Day 3 will be omitted and handled

as missing data, and the patient will have the catheter and CGM system removed. A new catheter will be inserted for use with the patient's own insulin pump.

After the Day 3 lunch meal procedures are completed (approximately 5 hours after the start of the lunch meal), the catheter and CGM system will be removed. A new catheter will be inserted for use with the patient's own insulin pump. However, if the patient plans to stay at the clinic until that evening (approximately 5:00 PM) for Day –1 procedures for the next period, the new catheter and reservoir will not be inserted until after the standardized dinner (at approximately 7:00 PM) is given (Day –1 for the following period).

Additionally, a macroscopic and microscopic check of the removed catheter and catheter tubing will be performed on site, ideally immediately after removing but within 120 minutes to exclude micro-occlusions and/or particles in the tubing.

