9.4.7.1. Subjective Procedure: Examination of Infusion Set and Catheter

When the infusion set and reservoir are changed (except for Period 1, Day -1) at the site, a macroscopic (visual) and microscopic examination (ideally immediately after removing the catheter, but no longer than 120 minutes) will be performed including the following:

- a check on the infusion set or the catheter for signs of kinking or other damage. In case of damage, the damage should be described in the CRF and photographic evidence should be taken
- a check of the insulin in the reservoir and infusion-set tubing for color change and crystals and/or particles including the location of these (that is, reservoir, infusion set)
- a microscopic check of the catheter tubing to exclude micro-occlusions and/or particles in the tubing

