9. STATISTICAL METHODOLOGY

9.1 General

Data listings will be provided for all data that is databased. Summary statistics and statistical analysis will only be presented for data where detailed in this SAP. For continuous data, summary statistics will include the arithmetic mean, arithmetic standard deviation, median, min, max and N; for log-normal data (e.g. the PK parameters: AUCs and C_{max}) the geometric mean and geometric coefficient of variation (CV%) will also be presented. For categorical data, frequency count and percentages will be presented. Data listings will be provided for all patients up to the point of withdrawal, with any patients excluded from the relevant population

highlighted. Summary statistics and statistical analyses will generally only be performed for patients included in the relevant analysis population. For the calculation of summary statistics and statistical analysis, unrounded data will be used.

Mean change from baseline is the mean of all individual patients' change from baseline values. Each individual change from baseline will be calculated by subtracting the individual patient's baseline value from the value at the timepoint. The individual patient's change from baseline values will be used to calculate the mean change from baseline using a **CCI** [REDACTED].

Unless otherwise specified, testing for significance is all done at an α -level of 0.1 with 2-sided confidence intervals (CIs). Statistical significance will be claimed if the p-value of a test is less than 0.1.

Data analysis will be performed using **CC** [REDACTED].

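### SAP 9.5.12 takes the catheter occlusion rate from a macroscopic CRF item, but the protocol endpoint is microscopic assessment

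*SAP*

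**What the plan says.** Protocol Table ITSC.4.1 lists, among the exploratory objectives, the determination of catheter occlusion rates with each insulin after 3 days of CSII. Its endpoint is "Microscopic assessment of infusion tubing after 3 days of use or in case of suspected catheter occlusion".

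Two procedure sections support this. Protocol 5.1.1.4 (Day 3 Activities) states that "a macroscopic and microscopic check of the removed catheter and catheter tubing will be performed on site", within 120 minutes of removal. Protocol 9.4.7.1 lists three checks:

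- "a check on the infusion set or the catheter for signs of kinking or other damage";
- a check of the insulin in the reservoir and tubing for colour change, crystals or particles;
- "a microscopic check of the catheter tubing to exclude micro-occlusions and/or particles in the tubing".

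SAP 4.3 repeats the objective. SAP 9.5.12 then takes the frequency of "occlusions observed on macroscopic examination of the catheter and catheter tubing" as the source of the rate. That sentence stops at "from the CRF will be", without its final verb. The section closes: "All other safety assessments not detailed in this section will be listed but not summarized or statistically analyzed".

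**The concern.** The SAP measures the objective with a different examination from the one the protocol names. Protocol 9.4.7.1 treats a macroscopic check as a visual one, so a small blockage or deposit could be seen under the microscope and missed by eye. The SAP would then report a rate of visible occlusions as the answer to an objective defined on microscopic findings. Nothing in the SAP would tell a reader of the report that the measure had changed.

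The objective is exploratory, and no test, margin or decision rule depends on it. Even so, Protocol 3.1 names compatibility, which it explains as catheter occlusions, as one of the kinds of data the trial is run to gather, alongside PK/GD and safety. The planned summary of it should measure what the protocol defined.

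**Working it through.** The plan gives no figure to reproduce for this endpoint: no expected occlusion rate, margin or power. The check is a comparison of texts, followed by a small calculation for scale.

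**Comparison**

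| Item | Protocol | SAP |
|---|---|---|
| Objective | Occlusion rates by insulin after 3 days of CSII (Table ITSC.4.1) | The same (4.3) |
| Source of the rate | Microscopic assessment (Table ITSC.4.1) | CRF item on macroscopic examination (9.5.12) |
| Examinations performed | Macroscopic and microscopic (5.1.1.4, 9.4.7.1) | Only macroscopic mentioned |
| Early examination for suspected occlusion | Part of the endpoint (Table ITSC.4.1) | Not addressed |

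1. The objective is the same in both documents, so the difference in source is not explained by a difference in question.
2. Of the three checks itemised in Protocol 9.4.7.1, only the microscopic one names occlusion.
3. SAP 9.5.12 details only the macroscopic item. Under its closing sentence, a microscopic result would be listed and not summarised.
4. The form of the summary can be inferred. SAP 9.5.12 refers to both insulins, and SAP 9.1 says: "For categorical data, frequency count and percentages will be presented". The denominator is not stated.
5. SAP Section 3 says that the SAP supersedes the protocol's statistical considerations and that substantial differences will be identified. This difference is not identified.

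**Weight of one catheter**

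Inputs: each of the four sequences in Table 1 of the SAP (Table ITSC.5.1 of the protocol) has two periods per insulin; one study catheter is scheduled per period; the target is 20 completers, from 24 patients enrolled initially.

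- Catheters per insulin with 20 completers: 2 × 20 = 40. One catheter: 1/40 = 2.5 percentage points.
- Catheters per insulin if all 24 finish: 2 × 24 = 48. One catheter: 1/48 = 2.08, or 2.1 percentage points.

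These counts exclude repeated periods, partial data from dropouts and replacement patients (enrolment may reach 30). If the unit were the patient, one affected patient would weigh 1/20 = 5.0 or 1/24 = 4.2 percentage points. These figures show how much one omitted finding moves the reported rate. They do not estimate the bias.

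**The case against.** The strongest reply is that macroscopic inspection is itself a planned occlusion check. The full sentence in Protocol 5.1.1.4 gives the exclusion of micro-occlusions and particles as the purpose of both examinations, and the list in 9.4.7.1 is introduced in a way that does not make it exhaustive. This stands as far as it goes: the macroscopic item has a basis in the protocol. It does not make that item the endpoint, which Table ITSC.4.1 defines as microscopic.

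Second, the SAP puts the phrase in quotation marks and attributes it to the CRF, so it may be a copied label, and the CRF or the TFL shells may hold a separate microscopic item or table. Neither is available, so this cannot be excluded; a simple slip of wording is also possible. In each case the SAP text still disagrees with the protocol and needs correction or explanation.

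Third, the rule in SAP Section 3 concerns statistical considerations in the protocol, and Protocol Section 10 contains no occlusion analysis. Whether the rule covers this endpoint is arguable, and the finding does not depend on it.

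Fourth, the objective is exploratory and any databased microscopic result would still appear in listings, so the data would not be lost. That limits the harm, but a reader would have to rebuild the rate from the listings. The missing verb may have been lost in text extraction and carries no weight here.

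**Conclusion.** The concern holds. As written, SAP 9.5.12 reports a different measure from the protocol's endpoint and plans no rate from the microscopic check. The total effect on the reported rates cannot be derived from the documents. Each occlusion seen only under the microscope and left out would lower that insulin's rate by 2.5 percentage points with 40 catheters, or 2.1 with 48. These weights assume the catheter as the unit and one scheduled study catheter per period.

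Confidence is high that the two texts disagree. What the final tables would show depends on the CRF and TFL shells, which were not available. The correction should be made, but it does not touch the primary inference.

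**What to change.** 1. Confirm that the CRF has a field for the microscopic result.
2. Complete the sentence in SAP 9.5.12 so that the occlusion rate is the count and percentage of examined study catheters with an occlusion on microscopic assessment, by insulin.
3. State the denominator, and say whether catheters examined early for suspected occlusion are counted with the 3-day catheters or shown apart. Limiting it to study catheters also keeps out any outpatient Humalog set changed on site on Day -1 of Periods 2 to 4, which a literal reading of Protocol 9.4.7.1 could bring in.
4. Report macroscopic findings separately.
5. If the macroscopic measure is intended, say so in the SAP as a departure from Table ITSC.4.1 and give the reason.

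The cost is one SAP sentence and one table. The protocol already requires the microscopic examination. Further work would arise only if the CRF proves to have no field for its result.

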10. INTERIM ANALYSES

No interim analyses are planned for this study. If an unplanned interim analysis is deemed necessary, the Lilly clinical pharmacologist, CRP, investigator, or designee will consult with the appropriate medical director or designee to determine if it is necessary to amend the protocol.

The Lilly clinical pharmacologist/CRP/Lilly study team is unblinded. Data may be accessed and analyzed while the trial is ongoing, but no changes to the study design are planned. The results may help Lilly expedite final delivery and enable planning of future studies. Information that may unblind the study during the analyses will not be reported to the study site until the study has been unblinded. An assessment committee will not be formed.

12. DATA PRESENTATION

12.1 Derived Parameters

Individual derived parameters (e.g. PK parameters) and appropriate summary statistics will be reported to three significant figures. Observed concentration data, e.g. C_{max} , should be reported as received. Observed time data, e.g. t_{max} , should be reported as received. N and percentage values should be reported as whole numbers. Median values should be treated as an observed parameter and reported to the same number of decimal places as minimum and maximum values.

12.2 Missing Data

Missing data will not be displayed in listings.

12.3 Insufficient Data for Presentation

Some of the TFLs may not have sufficient numbers of patients or data for presentation. If this occurs, the blank TFL shell will be presented with a message printed in the center of the table, such as, “No serious adverse events occurred for this study.”

13. BLINDING AND UNBLINDING PLAN

Levels of unblinding are indicated in the table below. This table provides general guidance as to who will be allowed access to blinding information (including data or documents that can potentially unblind such as randomization codes, treatment assignments, and unblinded data) at various steps of the trial. For Interim Analysis (IA), appropriate IA team members, including the statistician, programmer and data manager will be identified and agreed upon between Lilly and any relevant Third Party Organizations (TPO).

Blinding information is kept strictly confidential and is accessible only by authorized personnel until unblinding of the trial as described below. All measures possible must be taken to maintain the blind; which means that access to the blinding information must be restricted to authorized personnel as described in the protocol and summarized in the table below.

In case of an emergency, the investigator has the sole responsibility for determining if unblinding of a patient’s treatment assignment is warranted for medical management of the event. In such cases, the unblinding is to be conducted according to the protocol.

In the event of unplanned intentional unblinding, the detailed process, including information of the unblinded team, creating restricted access electronic folders, and measures taken to guard against inappropriate dissemination of treatment codes, will be described in a blinding plan revision or another appropriate document and review sought from the study team statistician.

Study Team Member	Study Timelines				
	Screening	Randomisation	Treatment Phase	Follow-Up	Database Entry Lock
General					
Clinical Supply Coordinator	NA	U	U	U	U
Randomization Statisticians	NA	U	U	U	U
ECG Reader	NA	U	U	U	U
Central Laboratory	NA	U	U	U	U
Local Laboratory	NA	NA	NA	NA	NA
Bio and Sample Analysis Lab	NA	U	U	U	U
Clinical Site					
Pharmacist	NA	U	U	U	U
Study/Dosing Nurse	NA	B	B	B	U
Technicians/Data entry staff	NA	B	B	B	U
Patient/Subject	NA	B	B	B	U
Investigator(s)	NA	B	B	B	U
Study Monitor (Covance)	NA	U	U	U	U
Covance Biometrics					
Project Integration	NA	U	U	U	U
Data Management	NA	U	U	U	U
Programming	NA	U	U	U	U
Statistician	NA	U	U	U	U
Medical Writing	NA	U	U	U	U
PK Scientist/Associate	NA	U	U	U	U
Lilly					
CP/CRP/CRS/Biologist	NA	U	U	U	U
Consultant CPM	NA	U	U	U	U
CPA / Study Manager	NA	U	U	U	U
DSA	NA	U	U	U	U
SDTM Core Team	NA	U	U	U	U
Statistician	NA	U	U	U	U
Statistical Analyst	NA	U	U	U	U
Medical Writing	NA	U	U	U	U
PK Scientist/Associate	NA	U	U	U	U
PK Analyst	NA	U	U	U	U
PK Data Delivery	NA	U	U	U	U
CLO Representative	NA	U	U	U	U

Abbreviations: B = blinded; CLO = clinical laboratory operations; CP = clinical pharmacologist; CPA = clinical pharmacology associate; CPM = clinical project manager; CRP = clinical research physician; CRS = clinical research scientist; DBL = database lock; DSA = data solutions associate; ECG = electrocardiogram; FPET = first patient enters treatment; LPET = last patient enters treatment; N/A = not applicable; PK = Pharmacokinetic; SDTM = study data tabulation model; TPO = third party organization; U = unblinded.
